2.0 PROTOCOL

2.1 Protocol Methodology and Analysis

Methodology:

Subjects are to be enrolled in this clinical study if they are a healthy male or female 18 years of age or older. Up to 50 subjects will be enrolled at 3 study centers. Subjects will be enrolled into 2

groups, Group A for TempSure treatments only and Group B for TempSure and Icon treatments. Randomization will not be required as subjects will only be enrolled in Group B and treated with the Icon device if they present with pigment and/r vascular lesions. Subjects will attend a screening/pre-treatment visit which may be performed on the same day as the treatment visit. Subjects in Group A will receive up to 4 treatments with the TempSure device on the face. Subjects in Group B will receive 2 treatments with just the TempSure device and 2 treatments with both the TempSure and Icon device. Some subjects may be asked to return for an optional 5th treatment (2 – 3 weeks post last treatment) with the Icon device (and/or TempSure device) after the completion of their 4 treatments at the discretion of the Investigator. Subjects may receive a phone call 1 week (1-7 days) after each treatment to record side effects. Subjects will return for follow up visits at 4 and 12 weeks post last treatment for efficacy and side effects assessments. An unscheduled visit or phone call may be performed at any time during the study at the request of the subject or as deemed necessary by the site Investigator.

Analysis:

Upcoming generations are proving to have an interest in non-ablative aesthetic treatments and will drive demand for innovated products, procedures, and practice design.¹ Due to this shift in patient base, practices need to evolve to adapt to the newer generational ideologies. There have been rapid advances in RF technology over the past few years and the nonsurgical treatment using this energy source offers great promise to our aging population.² Radiofrequency technology for the treatment facial wrinkles and skin laxity needs to be further investigated to optimize treatment parameters for safe and effective non-ablative aesthetic treatments.

Relevance:

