2.13 Evaluation Methods

Photographs:

Photographs will be taken at baseline and at the 4 and 12 week follow up visit, and may be taken at eat treatment visit to assess the efficacy and safety of treatment.

Treatment Discomfort/Pain Evaluation:

Subjects will be asked to report the general level of treatment discomfort on a scale of 0 (none) to 10 (maximum intolerable pain) using the universal pain assessment tool (Appendix B)

Fitzpatrick Wrinkle Severity Scale

The Fitzpatrick Wrinkle Severity Scale will be used to evaluate outcomes. Live evaluation will be performed at Baseline and the 4 and 12 week follow up visits. The results will be compared to determine improvement.

Class	Wrinkling	Score	Degree of Elastosis
I	Fine wrinkles	1-3	Mild (fine textural changes with subtly accentuated skin lines)
II	Fine to moderate-depth wrinkles, moderate number of lines	4-6	Moderate (distinct papular elastosis [individual papules with yellow translucency under direct lighting] and dyschromia)
III	Fine to deep wrinkles, numerous lines with or without redundant skin folds	7-9	Severe (multipapular and confluent elastosis [thickened yellow and pallid] approaching or consistent with cutis rhomboidalis)

Subject Treatment Questionnaire:

Subject treatment questionnaires may be collected from each subject to obtain feedback on their treatment experience.

Blinded Evaluation:

Three blinded independent reviewers will perform a photographic evaluation in which they will be asked to identify pre-treatment images when compared to post treatment images. The reviewers will be Board Certified Dermatologists and/or Surgeons and will be chosen based on availability and have relevant clinical experience. They will attend a training session prior to grading.

Physician and Subject Questionnaire:

The Global Aesthetic Improvement Scale (GAIS) ranging from “worse” to “very much improved” will be used to judge the improvement as seen by the subject and Investigator.

Global Aesthetic Improvement Scale Assessment	
Rating	Description
1	Very Much Improved- Optimal cosmetic result in this subject

2	Much Improved- Marked improvement in appearance from the initial condition, but not completely optimal for this subject.
3	Improved- Obvious improvement in appearance from initial condition, but a re-treatment is indicated.
4	No Change- The appearance is essentially the same as the original condition.
5	Worse- The appearance is worse than the original condition.

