2.15 Statistical Analysis**2.15.1 Hypothesis**

For this study to be considered a success, of pre-treatment images when compared to post treatment (90 day) images will be $\geq 80\%$.

For the additional assessments to be considered a success, the following must be true:

- In cases where the subject's improvement is being graded on a scale, such as the FWSS and GAIS scale, we will test the statistical significance of our results against a hypothetical population that would have no change (average score of 4).
- Subject treatment and clinician usability questionnaires are collected.
- The side effect profile (adverse events) and the average pain score is acceptable to the Physician as it relates to the type of treatment.

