2.15.2 Sample Size Rationale

Based on the need for data collected from this study, it was determined that a total of 50 subjects will be required, including departures.

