2.15.5 Analysis of Efficacy Variables

Additional efficacy variable is the change from baseline to Visit 7 (12 week follow up visit). Baseline is defined as the last assessment prior to the first treatment. The change from baseline to visits 6 and 7 will be analyzed using a Mixed Model Repeated Measures Analysis of Variance. A pairwise treatment group comparison at visit 7 will be performed using the results of this analysis. If a patient has no post-baseline assessment of the primary efficacy variable it will be assumed that the change from baseline to visit 7 is zero. The changes to visits 6 and 7 will be left as missing. Statistical significance with respect to the treatment group comparison at visit 7 will be declared if the two-sided p-value is < 0.05 . For each treatment group, summaries will be prepared for both the observed assessment and the change from baseline. The summaries will include the sample size, mean, median, standard deviation, minimum, and maximum. The statistical significance of the mean change from baseline for each treatment group will be determined using a paired t-test.

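### The additional-assessment success rule uses 4 as the no-change value for both FWSS and GAIS, but 4 means no change only on the GAIS

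*Combined protocol and SAP*

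**What the plan says.** Section 2.15.1 opens its list of conditions for the non-primary assessments with "For the additional assessments to be considered a success, the following must be true". The first condition covers outcomes graded on a scale, gives the FWSS and the GAIS as its examples, and states: "we will test the statistical significance of our results against a hypothetical population that would have no change (average score of 4". It names no test, alpha or direction for this comparison.

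Section 2.13 defines both scales:

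- **GAIS**, rated 1 to 5. Rating 4 reads "No Change- The appearance is essentially the same as the original condition".
- **FWSS**, scored 1 to 9 in three classes (1-3, 4-6, 7-9). A score of 4 is the bottom of Class II, described as "Fine to moderate-depth wrinkles, moderate number of lines". The scale is rated at baseline and at both follow-up visits, and "The results will be compared to determine improvement".

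Section 2.15.5 describes an analysis of change from baseline that includes this sentence: "The statistical significance of the mean change from baseline for each treatment group will be determined using a paired t-test". It does not name the FWSS and does not refer back to the rule in 2.15.1.

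On numbers, section 2.1 says "Up to 50 subjects will be enrolled at 3 study centers", and section 2.15.2 says "a total of 50 subjects will be required, including departures".

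**The concern.** The GAIS is itself a rating of change, so a fixed value can stand for no change. The FWSS is a rating of current severity. An unchanged subject who starts at 2 stays at 2, and one who starts at 7 stays at 7. No single FWSS score represents no change.

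No entry criterion in section 2.3 sets an FWSS score, so the cohort mean can fall on either side of 4. If the rule is followed as written, a cohort with mild wrinkles could show a significant FWSS result with no treatment effect. A cohort with deeper wrinkles could improve and still sit significantly on the wrong side of 4. Section 2.1 says the data are meant to support marketing claims, so an FWSS improvement statement resting on this rule would matter even though it is not the primary endpoint.

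**Working it through.** **1. Check the value 4 against each scale (section 2.13).**

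| Scale | Range | Meaning of 4 | Value representing no change |
|---|---|---|---|
| GAIS | 1-5 | No Change | 4 |
| FWSS | 1-9 | Lowest Class II severity score | Follow-up minus baseline = 0 |

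The stated value is reproduced for the GAIS and not for the FWSS. Nothing in the document defines an FWSS-derived improvement score on which 4 would mean no change. This step needs no assumptions.

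**2. Illustrate the consequence.** The plan gives no test, alpha, SD or baseline mean for this comparison. Assumed here: a one-sample t-test of follow-up FWSS against 4, two-sided 0.05, SD 1.5-2.0. Sample sizes are n = 50 (the planned total, which includes departures) and n = 25 (one group under an assumed even split).

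Noncentrality = (m − 4) / (SD/√n), where m is the true follow-up mean. Rejection probabilities come from the noncentral t with n − 1 degrees of freedom.

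*Ineffective device, so m equals the baseline mean. Probability of a mean significantly below 4:*

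| m | n | Noncentrality, SD 1.5 / 2.0 | Probability, SD 1.5 / 2.0 |
|---|---|---|---|
| 3 | 50 | −4.71 / −3.54 | 99.6% / 93.4% |
| 3.5 | 50 | −2.36 / −1.77 | 63.7% / 41.0% |
| 3.75 | 50 | −1.18 / −0.88 | 21.1% / 13.7% |
| 4 | 50 | 0 / 0 | 2.5% / 2.5% |
| 3 | 25 | −3.33 / −2.50 | 89.2% / 67.0% |
| 3.5 | 25 | −1.67 / −1.25 | 36.0% / 22.4% |

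For example, with m = 3, n = 50 and SD 1.5: (3 − 4)/(1.5/√50) = −1/0.2121 = −4.71.

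*Real improvement from 6 to 5, so m = 5.* Noncentrality is +4.71 / +3.54 at n = 50 and +3.33 / +2.50 at n = 25. The mean is significantly above 4 with probability 99.6% / 93.4% (n = 50) or 89.2% / 67.0% (n = 25).

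**3. The same 1-point improvement under a paired test against 0.** Noncentrality = −1/(SD of change/√n), with the SD of change assumed to be 1.0, 1.5 or 2.0.

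| n | SD 1.0 | SD 1.5 | SD 2.0 |
|---|---|---|---|
| 50 | −7.07; >99.9% | −4.71; 99.6% | −3.54; 93.4% |
| 25 | −5.00; 99.8% | −3.33; 89.2% | −2.50; 67.0% |

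Its type I error is 5% whatever the baseline mean.

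**4. The other literal reading: change scores tested against 4.** With zero true change and n = 50, the expected t is about (0 − 4)/(1.0/√50) = −28.3 at an SD of change of 1.0, and −14.1 at 2.0. The test would always reject. Neither literal reading gives a valid FWSS test.

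**The case against.** The strongest reply is that the plan already holds the right analysis. The 4 is a parenthesis that fits the GAIS anchor. Section 2.13 says FWSS results are compared over time, and 2.15.5 tests change from baseline. In the section 2.12 schedule the FWSS is the only efficacy scale with a baseline rating, so 2.15.5 has no other scale to act on. That is probably what was intended. But 2.15.1 names the FWSS explicitly and is the section that defines success, while 2.15.5 neither names the FWSS nor says that it takes precedence. Two different nulls stand, and choosing between them after the data are seen would not be prespecified.

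A second reply is that 2.15.1 only promises a test, without requiring a significant result, and concerns additional assessments. The limited scope is accepted. Even so, a test against the wrong value is wrong whether or not a pass mark is attached.

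A third reply is that the probabilities rest on assumed means and SDs. This stands. The near-certain error rates need a cohort mean a full point from 4; at 3.75 they fall to 21-14%, and at 4 they are nominal. The paired test is specified per treatment group, so the n = 50 paired figures are for a pooled version, and the even split behind n = 25 is an assumption because allocation depends on presenting lesions. At an SD of change of 2.0, paired power per group drops to 67%. None of this alters the mismatch of definitions, which needs no assumptions.

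**Conclusion.** The concern holds. For the FWSS, the no-change value in section 2.15.1 contradicts the scale's own definition in section 2.13, and section 2.15.5 does not cure it. The size of the error depends on where the cohort mean falls, which the plan does not fix. Under the assumptions above (n = 50, SD 1.5-2.0), an ineffective device gives a mean significantly below 4 in 14% to 99.6% of trials as the cohort mean moves from 3.75 down to 3. The primary endpoint and the GAIS comparisons are not affected. This should be corrected before analysis.

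**What to change.** In section 2.15.1, limit the value 4 to the GAIS. Suggested wording:

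> For PGAIS and SGAIS, the mean score is tested against 4 (No Change). For the FWSS, the null hypothesis is a mean change from baseline of 0, tested by the paired t-test in section 2.15.5.

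In the same edit:

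- Name the FWSS in 2.15.5.
- State the visit, the alpha and direction, and whether the test is run per group or pooled.
- State which FWSS grade enters the test. Section 1.2 lists photographic grading by three independent reviewers and section 2.13 lists live grading. Both can be done, but the plan does not say which one is tested. In an open-label study the independent photographic grade is the natural choice. The blinding described in 2.13 refers to identifying pre-treatment images, so it should be extended to FWSS grading explicitly. This is a related gap in detail; the main correction does not depend on it.

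The cost is a few sentences in 2.15.1 and 2.15.5. Baseline and follow-up FWSS ratings and photographs are already scheduled, so no new data are needed.

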1.2 Objectives

1. Primary Objective:
 - Photographic evaluation with correct identification of pre-treatment 2D images when compared to the 12 week follow up images performed by three independent reviewers.
2. Assessments:
 - Photographic evaluation with correct identification of pre-treatment 2D images when compared to the 4 week follow up images performed by three independent reviewers.
 - Photographic evaluation with Fitzpatrick Wrinkle Severity Scale (FWSS) grading comparing pre-treatment images to the 4 and 12 week follow up images performed by three independent reviewers.
 - Principle Investigator assessment using the Global Aesthetic Improvement Scale (GAIS) at the 4 and 12 week follow up visit.
 - Subject assessment using the Global Aesthetic Improvement Scale (SGAIS) at the 4 and 12 week follow up visit.
 - Subject Questionnaires
 - Pre-Treatment 1
 - Post Treatment 1
 - Follow Up
3. Safety Objectives:
 - Collection of Adverse Events
 - Collection of Treatment Discomfort/Pain Evaluation

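### The scale criterion in 2.15.1 requires that a significance test be run but requires no result from it, so read literally it is met whatever the data show

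*Combined protocol and SAP*

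**What the plan says.** Section 2.15.1 (Hypothesis) gives the study a primary success rule of at least 80% on the photographic comparison. It then opens a second list with "For the additional assessments to be considered a success, the following must be true". The list has three bullets:

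- **Scales (FWSS, GAIS):** "we will test the statistical significance of our results against a hypothetical population that would have no change", with 4 given as the average score of that population.
- **Questionnaires:** "Subject treatment and clinician usability questionnaires are collected".
- **Safety:** "The side effect profile (adverse events) and the average pain score is acceptable to the Physician as it relates to the type of treatment".

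Section 1.2 names the scale assessments: FWSS, investigator GAIS and subject GAIS, each at the 4-week and 12-week visits. The subject item, for example, reads "Subject assessment using the Global Aesthetic Improvement Scale (SGAIS) at the 4 and 12 week follow up visit".

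Section 2.15.5 makes the change from baseline to Visit 7 (12 weeks) an additional efficacy variable and contains two statements about significance. One is a decision rule for Group A versus Group B: "Statistical significance with respect to the treatment group comparison at visit 7 will be declared if the two-sided p-value is < 0.05". The other names a within-group test: "The statistical significance of the mean change from baseline for each treatment group will be determined using a paired t-test". The second sentence gives no significance level and does not mention success.

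**The concern.** A success criterion should turn data into a yes or a no. The scale bullet takes only one input, whether the test was performed. No p-value, direction, visit, scale or minimum improvement enters it.

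This is the only efficacy condition in the additional success list, and section 2.1 says the data are meant to support current and additional marketing claims. A criterion that no efficacy result can fail gives such a claim no support. If the sponsor instead intends that some significant improvement be shown, the plan does not say which one. It could then be chosen after the results are known, in an open-label study where section 2.15.3 also allows interim results to be reported.

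The point is separate from the reference value of 4. Correcting that value for FWSS would still leave a non-significant result satisfying the bullet.

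**Working it through.** **1. Does another section supply the missing result?**

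| Section | What it states | Tied to success of the additional assessments? |
|---|---|---|
| 2.15.1, scale bullet | A test against no change will be run | Yes, but no result is required |
| 2.15.2 | 50 subjects including departures; no alpha, power, effect size or SD | No |
| 2.15.4 | Two-sided p<0.05 for demographic and medical history comparisons | No |
| 2.15.5 | Two-sided p<0.05 for Group A versus Group B at Visit 7 | No; it does not test improvement over no change |
| 2.15.5 | Paired t-test of mean change within each group | No |

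No section fills the gap. The safety bullet in the same list does depend on an outcome (a judgement of acceptability); the scale bullet does not. The plan gives no operating characteristic for this criterion, so there is no stated figure to reproduce.

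**2. Literal reading.** Success on the bullet equals test performed. The probability of meeting it is therefore 1 under improvement, no change or worsening.

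**3. Charitable reading: at least one significant improvement.** Inputs: three scales and two visits (section 1.2) give 3 × 2 = 6 tests, and two groups give 12. Total n is 50 (section 2.15.2). Assumptions: 25 per group, equal correlation between tests within a group of 0 to 0.8, and no true effect. A two-sided 5% test has a 2.5% chance of a false result in the improvement direction. For k independent tests the chance of at least one is 1 − 0.975^k:

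- k = 6: 1 − 0.975^6 = 0.141
- k = 12: 1 − 0.975^12 = 0.262
- k = 3 (Visit 7 only): 1 − 0.975^3 = 0.073

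Simulating one-sample t-tests (40,000 null trials per setting) gives:

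| Tests | Correlation 0 | 0.3 | 0.5 | 0.8 |
|---|---|---|---|---|
| Six, n=50 | 14% | 12% | 10% | 7% |
| Twelve, 25 per group | 26% | 23% | 20% | 14% |
| Three at Visit 7, n=50 | 7% | 7% | 6% | 5% |

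The comparator is 2.5% for a single named test.

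**4. What an outcome rule would demand.** With n=50 the critical t is 2.010. For GAIS, where 4 means no change and lower is better, the observed mean must be at or below 4 − 2.010 × SD/√50. That is 3.86, 3.79 or 3.72 for an assumed SD of 0.5, 0.75 or 1.0. The chance of passing is then 2.5% if the true mean is 4.0, 41% to 93% if it is 3.75 (SD 1.0 to 0.5), and at most 0.01% if it worsens to 4.25.

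**5. Power for an assumed 0.5 SD shift** (noncentral t, noncentrality 0.5√n):

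| Evaluable | One test | Two independent tests, both required |
|---|---|---|
| 50 | 93% | 0.934² = 87% |
| 40 (assumed) | 87% | 0.869² = 76% |

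**The case against.** The strongest reply is that this is loose drafting. The bullet sits under a hypothesis heading, follows a statement of what must be true, and compares results with a no-change population. Its authors probably meant that a significant improvement is needed, so a pass probability of 1 describes the wording and not what the sponsor would do. That is fair on intent. It does not settle which scale, visit or direction counts.

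Section 2.15.5 also narrows the menu. It singles out Visit 7, names a within-group test, and 0.05 two-sided is the only significance level in the plan. This stands in part: it is why the three-test figure of 7% to 5% is shown. But the section does not connect any of this to the success rule.

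A reader might infer false-positive rates about twice as large, roughly 27% to 14% for six tests and 46% to 27% for twelve. Those count significant worsening as success, which no sensible reading intends, so the improvement-only figures are the right ones.

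A reader might also infer that the additional assessments cannot fail, or that study success is affected. The documents support neither. The safety bullet can fail the list, and the primary 80% rule is stated separately.

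**Conclusion.** The point holds for the scale bullet in 2.15.1. As written it is a decision rule that no scale result can fail, and nothing elsewhere in the plan repairs it. The consequence is confined to the secondary success claim.

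The literal result follows from the text and needs no assumption. The rates under the charitable reading rest on the assumed correlations, normal-theory t-tests and, for twelve tests, an assumed equal split between groups. If Visit 7 is taken as the focal visit, the inflation over 2.5% is modest; if both visits and both groups are open to choice, it is several-fold. The change is worth making because it is cheap and the criterion currently carries no efficacy information.

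**What to change.** Replace the scale bullet with an outcome rule, fixed before any follow-up data are reviewed, that states:

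- the scale or scales that must pass. The choice is the sponsor's; section 3.2 says investigator-assessed improvement is not an objective, which bears on investigator GAIS;
- for FWSS, which rating is used, since section 1.2 describes photographic grading by three reviewers and section 2.13 describes live evaluation;
- the 12-week visit;
- improvement at two-sided p<0.05, so that significant worsening cannot count;
- the null value for each scale: mean change from baseline against 0 for FWSS, and mean below 4 for GAIS. On the 1 to 9 FWSS, 4 is a severity level. An unchanged population with mean 3 or 5 would differ significantly from 4 in at least 93% of trials (n=50, assumed SD 1 to 2);
- whether the test is on all subjects or by group.

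If more than one scale is named, require all to pass; no multiplicity adjustment is then needed. Label the 4-week and remaining scale results supportive.

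The cost is a sentence or two in 2.15.1 and no new data, because the schedule already collects FWSS at baseline and both scales at 12 weeks. The downside is that the scale criterion can now fail. Since the 50 subjects include departures, power should be judged on the number evaluable: requiring two scales lowers it from 93% to 87% with 50 evaluable, and from 87% to 76% with an assumed 40, for a 0.5 SD shift and independent tests.
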